### **3 Introduction**

This Statistical Analysis Plan (SAP) is based on the current trial protocol (Amendment 3, 22Apr2016) and CRF (version 1, 28Sep2015). Where statistical methods differ substantially between this SAP and the protocol, that will be identified in this document.

This SAP describes the datasets and the statistical methods to be used for the reporting and analysis of all data collected during the trial except then genetics sample data.

If a future protocol amendment necessitates a substantial change to the statistical analysis of the trial data, this SAP will be amended accordingly. If, after database lock, additional analyses are required to supplement the planned analyses described in this SAP, those unplanned analyses will not be described in an amended SAP, but they will be identified in the integrated clinical trial report (CTR). Any deviations from this SAP will be documented in the CTR.

This SAP has been written in consideration of the following guidelines:

- International Conference on Harmonization (ICH) E9, Guidance for Industry: Statistical Principles for Clinical Trials (ICH E9 1998); and
- ICH E3, Guidance for Industry: Structure and Content of Clinical Study Reports (ICH E3 1995).

Statistical analysis will be done using SAS® 9.3 on a Windows PC.

### **4 Study Objective(s) and Endpoint(s)**

#### **4.1 Study Objective(s)**

##### **4.1.1 Primary Objective(s)**

To compare the uptake of [C]-GSK2256098 in the heart and lungs of PAH patients versus the heart and lungs of healthy control subjects

##### **4.1.2 Exploratory Objective(s)**

To explore the spatial distribution of [C]-GSK2256098 uptake in the heart and lungs of PAH patients versus the heart and lungs of healthy control subjects.

## **4.2 Study Endpoint(s)**

### **4.2.1 Primary Endpoint(s)**

Uptake of [C]-GSK2256098 in the heart and lung (assessed as the volume of distribution (VT) and/or standardised uptake values (SUV)) as measured by PET

### **4.2.2 Exploratory Endpoint(s)**

Qualitative assessment of the spatial distribution of [C]-GSK2256098 uptake in the heart and lungs

## **4.3 Statistical Hypotheses**

No formal statistical testing will be done. Instead an estimation approach has been adopted. Simple Bayesian methods will be used to quantify the evidence which the study generates about the endpoints themselves, and about contrasts (probability ratios) of these endpoints.

## **5 Study Design**

This is cross-sectional study exploring the uptake of [C]-GSK2256098 in PAH patients and in healthy (age and gender-matched) volunteers.

It is a non-randomised, open label study where all volunteers will receive one microdose of the radiolabelled compound.

Up to 12 healthy subjects and 12 PAH patients (including those with a prolonged QTcF interval  $\leq$  500ms) will be enrolled to provide sufficient PET data to quantify the uptake of [C]-GSK2256098 in the heart and lungs.

## 6 Time and Events Table

Procedure	Screening (up to 30 days prior to scan)	Scanning visit	Follow-up (2-4 weeks post-last dose)	Notes
Informed consent	X			
Inclusion and exclusion criteria	X			
Demography	X			
Brief physical	X	X	X	On the scanning day, to be completed pre-scan, prior to the administration of the peptide.
Medical / Medical history	X			
Vital signs	X	X		On the scanning day, to be conducted pre and post scan.
12-lead ECG	X			
Alcohol breath test	X	X		
Urine drug and cotinine screen	X			
Healthy subjects only: spirometry	X			
Coagulation profile	X			This will include PT (Prothrombin time), APTT (Activated Partial Thromboplastin Time) and Thrombin Time (TT)
PAH patients only (who have been on Warfarin): INR		X		Sample to confirm suitability for scanning day can be done up to 3 days prior to the day of the scan
HIV, Hep B and Hep C screen	X			If test otherwise performed within 3 months prior to first dose of study treatment, testing at screening is not required
Clinical chemistry and Haematology	X			
Urinalysis	X			
Allen's test	X	X		
i.v dose of [  C]-GSK2256098		X		
PET scan		X		PET scanning will be started at the same time as injection of the radioligand and PET data will be collected for up to 90 minutes post administration.

Procedure	Screening (up to 30 days prior to scan)	Scanning visit	Follow-up (2-4 weeks post-last dose)	Notes
Attenuation CT scan		X		Lasting seconds to minute prior to start of PET scan. If subject gets off the bed for a comfort break midway through the PET scan, another CT scan will be performed prior to re-starting acquisition of PET data
Genetics sample		X		Genetic Informed consent must be obtained before collecting a sample
Samples for plasma radioactivity measurements & whole blood		X		Blood samples will be collected during scanning for plasma and whole blood radioactivity measurements.
AE/SAE review		X	X	
Concomitant medication review	X	X	X	

## 7 Planned Analyses

### 7.1 Interim Analyses

No formal interim “testing” of any statistical hypothesis will be performed.

The strength of evidence in the PET data (about differential expression levels between patients and HVs) will be reviewed once five patients and five healthy volunteers have been studied in the PET scanner, and the relevant functional endpoints have been derived by Imanova scientists for heart chamber and whole lung regions. From that point onwards, the data will be monitored continuously (or as near as possible given practicalities of study operationalisation)

## 7.2 Final Analysis

The database will be locked once all subjects have completed the study, data have been entered and all queries resolved. The final analysis will be carried out following database lock.

## 8 Sample Size Considerations

There is little known about the likely mean values of the PET-derived functional primary endpoints (Volume of distribution, and/or some form of integrated SUV) in this

population. Therefore our sample size is driven by a mixture of:

- (i) what is known about between-subject variability from relevant, recent PET studies,
- (ii) feasibility, and
- (iii) flexibility.

An ongoing study investigating the validation and dosimetry of a PET ligand in healthy subjects and patients with IPF (study RES116235) has been able to draw firm conclusions about similar endpoints (in terms of the estimation methods we describe below) using around 5 subjects. Therefore we will set five patients and five age-matched HVs as our initial target sample size.

From that point onwards, the data will be monitored continuously (or as near as possible given practicalities of study operationalisation), and at each step the following decisions will be made:

- Stop, and conclude that there is strong evidence of differential FAK expression (as measured by the study endpoints) between patients and HVs.
- Stop, and conclude that there is insufficient evidence of any great difference, and furthermore (conditional on observed data i.e. in a formal Bayesian sense) there is low probability that an increase in sample size will reverse such a conclusion
- Continue to enrol patient-HV pairs, and re-evaluate the decision.

This iterative cycle will be followed up until a maximum of twelve patients and twelve HVs have been recruited into the study.

## **8.1 Sample Size Re-estimation or Adjustment**

The first statistical evaluation of the data will occur once five patients and five healthy volunteers have been studied in the PET scanner, and the relevant functional endpoints (such as  $V_T$ ) have been derived from their scan data by Imanova scientists. At this point, the statistical analysis (set out below) will be carried out, and, based on those results, the team may decide to recruit more subjects, up to a total of twelve patients and twelve healthy volunteers.

## **9 Analysis Populations**

The following populations will be identified:

Screened Population: all subjects who signed an informed consent form and were evaluated for study participation.

Safety Population: All patients and subjects who received the microdose of study drug.

The primary endpoint will be analysed using the Safety Population.

### **9.1 Analysis Datasets**

All analysis datasets will be based on observed data, except as outlined in Section 12.2.

## **10 Treatment Comparisons**

The comparison of interest is uptake of [C]-GSK2256098 in PAH patients versus healthy volunteers.

## **11 General Considerations for Data Analyses**

### **11.1 Data Display Group Descriptors**

The sort order for groups will be PAH patients then healthy control subjects. When a total column is included, it immediately follows the groups which it aggregates.

Listings of data will be sorted and displayed by group, subject number, and also by date and time if applicable.

The group descriptions to be used on all tables and listings are:

#### **Groups**

PAH Patients  
Healthy Volunteers

## 11.2 Conventions for Summary Statistics and Data Displays

The minimum set of summary statistics for numeric variables will be: n, mean, standard deviation (or standard error), median, minimum and maximum

Categorical data will be summarised in frequency tables with n and percentage. Summaries of a categorical variable will include all recorded values.

The minimum and maximum values will be presented with the same number of decimal places as the raw data collected on the CRF (or to 3 significant figures for derived parameters). The mean and percentiles (e.g. median, Q1, and Q3) will be presented using one additional decimal place. The standard deviation and standard error will be presented using two additional decimal places.

## 12 Data Handling Conventions

### 12.1 Premature Withdrawal and Missing Data

All subjects who withdraw prematurely from the study or study drug will be included in the statistical analyses.

If a subject completes the treatment period but has missing data, then this will be made apparent in the subject listings. Missing data will not be imputed except for as outlined in Section 12.2.

If the study is prematurely discontinued, all available data will be listed and a review will be carried out to assess which statistical analyses are still considered appropriate.

Data collected at unscheduled time points during the study will not be used in the summaries or data analyses. They will be included in the listings.

If time information (i.e. hours and/or minutes) for adverse events or concomitant medication is missing, but the day is present, then the time will be calculated in days. If date information is partial or missing, then any derived times (e.g. AE start time from last study medication) will be listed as missing.

### 12.2 Derived and Transformed Data

$V_T$  and mean SUV will be derived by Imanova for regions including heart chamber and whole lung.

The CT images obtained for attenuation correction (AC) of the PET [CT-AC)] are used to delineate the left and right lung and both the CT-AC and the region of interest (ROI) image are resampled to the PET space. Time activity curves are extracted using the predefined ROI image. Standardized uptake values (SUV) are generated by averaging the time activity curves between two time points (to be defined depending on the kinetics of the tracer in the lungs) and normalising to the injected dose per unit mass.

An image derived input function is generated using a region of interest in the pulmonary artery. This input function is used together with a compartmental model to derive the volume of distribution ( $V_T$ ) in each region of interest.

### **12.3 Assessment Windows**

No assessment windows are defined for this report.

### **12.4 Values of Potential Clinical Importance**

Any laboratory value outside the reference range for that variable (Appendix B) will be flagged as a value of a potential clinical importance

A vital signs result will be considered to be of potential clinical importance if it falls outside the relevant range below:

Vital Sign	Range
Supine/semi-recumbent systolic blood pressure	85–160 mm Hg
Supine/semi-recumbent diastolic blood pressure	40–90 mm Hg
Supine/semi-recumbent heart rate	40–100 beats/min
Respiration rate	8–20 per min
Oral temperature	35.5–37.8°C

## **13 Study Population**

### **13.1 Disposition of Subjects**

All analyses will use the safety population.

The disposition of all subjects (patients and healthy volunteers) in the safety population will be summarised including number of subjects screened, the number of subjects who failed screening, number completing the study by group, and number withdrawn from the study.

All subjects who withdraw or are withdrawn from the study will be listed by treatment, with the reason for withdrawal.

A listing of analysis populations will be provided.

## **13.2 Protocol Deviations**

Before closing the database, data listings will be reviewed to identify any significant deviations and determine whether the data should be excluded from any analysis populations.

Major protocol deviations include subjects who:

- Entered the study even though they did not satisfy the entry criteria.
- Met the criteria for withdrawal from the study but were not withdrawn.
- Received the wrong treatment or incorrect dose.
- Received an excluded concomitant therapy.
- Received investigational product(s) past the expiration date.
- Healthy volunteers who are not matched to a PAH patient on gender or with age not within  $\pm 5$  years

A summary table of the important deviations will be provided.

A listing of inclusions/ exclusion deviations will be provided.

A listing of all important deviations will be provided.

## **13.3 Demographic and Baseline Characteristics**

Demographic and baseline characteristics (e.g. physical examination, vital signs, Allen's test and INR) will be listed and summarised. A summary of age ranges of subjects will be presented.

A summary of the difference in ages between the matched pairs will also be presented.

Subjects who take concomitant medication will be listed. All non-trial medication will be coded by GSK.

## **13.4 Treatment Compliance**

Dates and times of dosing will be listed (Listing 16.2.1.1).

# **14 Safety Analyses**

The dates and times of treatment dosing will be listed to indicate exposure to the study medication (Listing 16.2.1.1).

## **14.1 Adverse Events**

Adverse events will be coded by GSK.

All adverse events will be listed. Subject numbers for specified adverse events will be listed. A listing of the relationship between system organ class and verbatim text will also be presented.

The number of subjects with at least one treatment-emergent adverse event (TEAE) will be tabulated by actual treatment and MedDRA system organ class. A treatment-emergent adverse event is defined as an event emerging during treatment having been absent pre-treatment or having worsened relative to pre-treatment.

For each of the following, the number of subjects with adverse events will be summarised:

- TEAEs by system organ class and preferred term
- IMP-related (as recorded by the Investigator) TEAEs by system organ class and preferred term

Subjects with more than one TEAE will be counted only once, at causality, for each system organ class/preferred term. Multiple TEAEs in a subject will be counted once per system organ class and preferred term. Adverse events with missing severity and/or causality will be treated as severe and related to IMP, respectively.

Summaries will be sorted by system organ class and decreasing total incidence of preferred term.

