## 6. STUDY TREATMENT

### 6.1. Investigational Product and Other Study Treatment

The term 'study treatment' is used throughout the protocol to describe any combination of products received by the subject as per the protocol design. Study treatment may therefore refer to the individual study treatments or the combination of those study treatments. In this study, the 'study treatment' is considered a microdose.

Product Name:	[  C]-GSK2256098 Injection
Formulation description:	Up to 5% Ethanol in saline
Dosage Form:	IV
Unit dose strength:	Up to 500 MBq of [  C]-GSK2256098
Route:	IV / single dose
Unit mass:	< 10 µg of GSK2256098
Administration:	Intravenous bolus over about 30 seconds
Physical description:	IV infusion, 20 mL
Manufacturer / source of procurement:	Imanova, London, UK 

1. According to the appropriate current Good Manufacturing Practice (cGMP) guidelines for the preparation of radio-pharmaceutical products to be administered to humans.

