#### 7.3.1.1. Time period and Frequency for collecting AE and SAE information

- Any SAEs assessed as related to study participation (e.g., protocol-mandated procedures, invasive tests, or change in existing therapy) or related to a GSK product will be recorded from the time a subject consents to participate in the study up to and including any follow-up contact.
- AEs will be collected from the start of the PET scan until the follow-up contact (see Section 7.3.1.3), at the timepoints specified in the Time and Events Table (Section 7.1).
- Medical occurrences that begin prior to the start of study treatment but after obtaining informed consent may be recorded on the Medical History/Current Medical Conditions section of the CRF.
- All SAEs will be recorded and reported to GSK within 24 hours, as indicated in [Appendix 3](#).
- Investigators are not obligated to actively seek AEs or SAEs in former study subjects. However, if the investigator learns of any SAE, including a death, at any time after a subject has been discharged from the study, and he/she considers the

event reasonably related to the study treatment or study participation, the investigator must promptly notify GSK.

NOTE: The method of recording, evaluating and assessing causality of AEs and SAEs plus procedures for completing and transmitting SAE reports to GSK are provided in [Appendix 3](#).

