## **16.2 Table of Contents for Data Display Specifications**

For overall page layout refer to Appendix A.

The numbering in the tables below will take precedence over the numbering in the shells.

The following tables and figures will be produced (templates provided in Section 16.2 and 16.3):

The following tables and figures will be produced (templates provided in Section 16.2.1 and 16.2.2):

Table	Description	Population	Source Listing	Template (Shells below)
10.1	Summary of Subject Disposition	Screened	16.2.1.2, 16.2.3.1	T_SD1
10.2	Summary of Important Protocol Deviations	Safety	16.2.2.2	T_DV_GK
14.1	DEMOGRAPHIC DATA			
14.1	Summary of Demographic Characteristics	Safety	16.2.4.1	T_DM1_PG
14.2	Summary of Age Ranges	Safety	16.2.4.1	T_AGE_GSK
14.3	Summary of Age Matching	Safety	16.2.4.1	T_DM2
14.3	SAFETY DATA			
14.3.1.1	Summary of Treatment-Emergent Adverse Events	Safety	16.2.7.1	T_AE1
14.3.1.2	Summary of Drug-Related Treatment-Emergent Adverse Events	Safety	16.2.7.1	T_AE1
14.3.2	Summary of Serious Adverse Events by System Organ Class and Preferred Term (Number of Subjects and Occurrences)	Safety	16.2.7.1	T_AE2
14.3.3	Narratives of deaths and other serious adverse events	Safety	16.2.7.1	-
14.3.4	Summary of Vital Signs at Scanning Visit	Safety	-	T_VS1
14.4	PET DATA			
14.4.1	Summary of Volume of Distribution ( $V_T$ ) and Mean Standardised Uptake Values (SUV), by Group and Region	Safety	16.2.9.1	T_PT1_GK
14.4.2	Summary of the Posterior Distribution for Volume of Distribution ( $V_T$ ) and Mean Standardised Uptake Values (SUV), by Group and Region	Safety	16.2.9.1	T_PT2_GK
14.4.3	Summary of the Posterior Distribution of the Ratio of Group Means for Volume of Distribution ( $V_T$ ) and Mean Standardised Uptake Values (SUV), by Region	Safety	16.2.9.1	T_PT3_GK
14.4.4	Posterior Probability that the Ratio of Group Means for Volume of Distribution ( $V_T$ ) and Mean Standardised Uptake Values (SUV) Exceeds a Certain Value, by Region	Safety	16.2.9.1	T_PT4_GK

Figure	Description	Population	Source Listing	Template (Shells below)
14.1	PET DATA	Safety		
14.1.1.1	Plot of the Posterior Distribution of the Volume of Distribution ( $V_T$ ) for the Group Means and the Ratio of the Group Means, by Region	Safety	16.2.9.1	F_PT1_GK

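### SAEs in consented subjects who are never injected are collected under the protocol but fall outside the SAP's SAE table and narratives

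*SAP*

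**What the plan says.** **Collection (protocol).** Section 7.3.1.1 covers SAEs judged related to taking part, with study procedures, invasive tests and changes to existing treatment as its examples. These "will be recorded from the time a subject consents to participate in the study up to and including any follow-up contact". Section 5.3 defines screen failures as people who consent but are never scanned, and includes SAEs in the minimum data required for them. Non-serious AEs are collected from the start of the PET scan to the follow-up contact.

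**Reporting (SAP).** Section 9 gives "Safety Population: All patients and subjects who received the microdose of study drug". Section 13.1 adds "All analyses will use the safety population". In the display contents (16.2), Table 14.3.2 (SAEs by system organ class and preferred term) and entry 14.3.3, "Narratives of deaths and other serious adverse events", both carry the population label Safety. The contents table for listings, which includes 16.2.7.2 (SAEs) and 16.2.7.5 (reasons for seriousness), has no population column. Section 14.1 says "All adverse events will be listed".

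**AE tables (SAP 14.1).** Both AE tables count treatment-emergent events only; the second is "IMP-related (as recorded by the Investigator) TEAEs by system organ class and preferred term". The definition is "A treatment-emergent adverse event is defined as an event emerging during treatment having been absent pre-treatment or having worsened relative to pre-treatment". The dose is given in protocol 6.1 as "Intravenous bolus over about 30 seconds".

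**The concern.** The collection rule starts at consent, while the reporting rule starts at the dose. In most microdose studies little happens between the two. Here two things do. Protocol 4.5.1 names arterial cannulation as a procedural risk and describes stopping or substituting warfarin beforehand to allow it. A subject can go through either step and then not be injected.

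If a study-related SAE occurred in such a subject, the sponsor would hold the record, but the two displays a reader would consult for serious events would not show it. With a ceiling of 12 patients and 12 healthy volunteers, apart from replacements, a single omitted procedure-related SAE could change how the safety of the study is described.

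**Working it through.** The plan states no figure on this point, so the check sets the rules side by side and follows one subject through them.

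**1. Can a subject be exposed to study-driven risk and remain undosed?** Yes, on the documents' own sequence.
- Protocol 4.5.1: warfarin is stopped about 5 days before cannulation, or replaced by low-molecular-weight heparin starting up to 5 days before.
- Protocol 7.1: INR is then checked to confirm suitability, with the sample allowed up to 3 days before the scan. The Allen's test and alcohol breath test are repeated at the scanning visit.
- Protocol 7.3.7: the arterial cannula is placed before the scan starts, and the scan starts with the injection.

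The anticoagulant change, the suitability checks and the cannulation all come before the dose.

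**2. Where does an SAE in that subject go?**

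| Rule | Source | Undosed subject included? |
|---|---|---|
| Participation-related SAEs recorded from consent | Protocol 7.3.1.1 | Yes |
| SAE data for consented, never scanned | Protocol 5.3 | Yes |
| SAE Table 14.3.2 | SAP 9, 16.2 | No |
| Narratives, 14.3.3 | SAP 9, 16.2 | No |
| SAE listings 16.2.7.2, 16.2.7.5 | SAP 13.1, 14.1, 16.2 | Unclear |

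The listings are unclear because 14.1 promises a listing of all AEs and 16.2 sets no population for listings, while 13.1 assigns every analysis to dosed subjects.

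**3. What about dosed subjects?** SAP 14.2 summarises SAEs without a treatment-emergent filter. Once a subject is dosed, a recorded SAE counts in Table 14.3.2 whether it arose at the warfarin change, at cannulation or weeks later. The gap is confined to undosed subjects.

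**4. How many people could that be?** The documents give no non-injection rate. As an assumption only, take 5% to 15% of 24 scheduled subjects:
- 24 × 0.05 = 1.2
- 24 × 0.15 = 3.6

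That is about 1 to 4 people. It does not estimate missed SAEs, which would need a further, unstated probability of a study-related SAE. Only patients taking warfarin face the anticoagulant change.

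**5. The treatment-emergent window.** AE collection runs from injection to follow-up at 2 to 4 weeks, so 14 × 86,400 = 1,209,600 s to 28 × 86,400 = 2,419,200 s. The share covered depends on what treatment means:
- Bolus only, 30 s: 30 / 1,209,600 = 0.0025% and 30 / 2,419,200 = 0.0012%.
- Full 90-minute scan, 5,400 s: 0.45% and 0.22%.
- From the dose onward: 100%, because protocol 7.1 starts the scan at the same time as the injection.

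The term removes almost everything or nothing. SAP 12.3 defines no assessment windows, and the treatment period mentioned in SAP 12.1 is not defined either.

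**The case against.** **A dosed-only safety denominator is legitimate.** This stands for Table 14.3.2. Its shell reports percentages of N, and moving it to all screened subjects would add screen failures who had no cannulation and no change of therapy, diluting the rates.

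**The data are not lost.** All AEs are to be listed, the SAE listings carry no stated restriction, and the SAP already departs from its own 13.1 rule by putting Table 10.1 on the Screened Population. SAEs also go to the sponsor within 24 hours. In so small a study one event in a listing would be seen. Much of this stands: it makes the point one of reporting, not of data loss. It does not help the narratives, which are labelled Safety, and it leaves the scope of the listings to whoever programs them.

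**A stronger reading: delayed AEs are left out of the tables.** A reader might infer this from the 30-second bolus, but the documents do not support it. The SAP never equates treatment with infusion time. Its definition is a stock one footnoted to ICH E9, contrasts with pre-treatment and excludes nothing after the dose. Since AE collection starts with the injection, the ordinary reading drops nothing. The mock AE listing even marks an event 10 days after the last dose as treatment emergent. That is weak evidence, because the exposure shell still shows oral tablets over 46 days. What stands is an undefined end point.

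**A second stronger reading: SAEs from cannulation or warfarin changes generally vanish.** They do not. In anyone who is later dosed, they are tabulated.

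**Conclusion.** The narrower point holds. Followed as written, the plan leaves a study-related SAE in a consented but uninjected subject out of Table 14.3.2 and out of the narratives, and does not say whether the SAE listings would show it. The protocol requires the same event to be collected.

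The gap is small in expected numbers: it needs both a missed injection and a study-related SAE, and the documents give a rate for neither. It has no bearing on the primary PET comparison. The conclusion rests on the population labels in SAP 9 and 16.2 and on the pre-dose sequence in the protocol, not on any assumed rate.

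The treatment-emergent wording needs clarifying only; it does not show that AEs are omitted.

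**What to change.** - **SAP 14.2 and 16.2.** Set the population for the 14.3.3 narratives and for Listings 16.2.7.2 and 16.2.7.5 to all consented subjects (the Screened Population), with a dosed/undosed flag. The contents table cites Listing 16.2.7.1 as the source for the narratives, so either extend that listing in the same way or cite 16.2.7.2.
- **SAP 13.1.** Exempt these displays from the rule that every analysis uses the Safety Population.
- **Table 14.3.2.** Keep the dosed-subject denominator. Add a footnote or separate count of SAEs in consented but undosed subjects.
- **SAP 14.1 (minor).** State that treatment-emergent means onset or worsening from the start of injection through the follow-up contact.

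The cost is SAP wording, one flag and possibly a few extra listing rows, in which the time-since-last-dose field is blank for undosed subjects. No new data are needed, because the protocol already collects these SAEs, and no study procedure changes.
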